#### 10.4 Blinding

The trial allocations cannot feasibly be blinded, and therefore this is designed as an open label trial. Adjudication of postoperative myocardial infarction, cerebrovascular accident, infectious and renal outcomes will be blinded, nonetheless.

#### 10.5 Participants lost to follow-up (6 month follow-up)

Site staff should make all reasonable effort to contact participants for the 6 month follow-up visit. In the event that a participant is lost to follow-up, this information will be recorded in the participant research chart and this should be captured in the eCRF in either the 'Hospital Summary' form or the '6 Month Follow-Up' form.

#### 10.6 Premature Discontinuation

Participants have the right to discontinue from the trial or trial transfusion strategy for any reason, at any time, without compromising the medical care they will receive in relation to the trial. All participants who are randomised and undergo surgery will be followed-up for the remainder of the trial up to the 6-month outcome, unless the participant withdraws consent for follow-up.

Any participant who is randomised but for any reason does not undergo surgery will not be followed-up and data will not be collected longitudinally. In this situation, the participant will be replaced to achieve the required sample size.

In both these instances, any data collected until this point will be retained, analysed and used in the final analysis, but no further data will be collected. In addition, the investigator may discontinue a participant from the trial at any time if the investigator considers it necessary, where the above in relation to data collection will also apply.

Sites will be required to complete the 'Hospital Summary' e-CRF with 'did not complete study' for the patient status field. The AHRC Data Coordinating Centre will query as required.

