#### 16.2 Analysis population

The ITT population consists of all patients who underwent randomisation and subsequent cardiac surgery with available outcome data.

The per-protocol (PP) population consists of all participants who underwent randomisation and subsequent cardiac surgery with cardiopulmonary bypass with available outcome data, except for patients who had a protocol adherence of less than 90%, patients who were withdrawn from the trial by the treating physician at any time, and patients who withdrew consent.

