#### 16.9 Missing Values

While we anticipate that the primary outcome will be available in >95% of patients, if the primary outcome is missing in more than 5% of patients, we will perform analyses to mitigate the effect of missing data as follows: we will develop a missing data model and perform a multiple imputation analysis. We will also carry out inverse-probability weighting. This is a two-stage model where a logistic regression model is first used to estimate the probability of not being missing. Then the analysis of the outcome proceeds on complete cases through a weighted analysis where the inverse probability of "completeness" forms the weights. The inference of the imputed model and inverseprobability weighting will be compared to that of the model with missing data.

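### Investigator withdrawal can end outcome collection in an open-label trial, and the set called ITT keeps only patients with outcomes, so the primary analysis may lose patients selectively by arm

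*Protocol*

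**What the plan says.** Three parts of the protocol bear on this.

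**Follow-up (10.6, repeated in 18.1.2).** The general rule reads "All participants who are randomised and undergo surgery will be followed-up for the remainder of the trial up to the 6-month outcome". Its one exception is a participant's own withdrawal of consent to be followed. Section 18.1.2 lists this among the steps against bias and gives no exception for the investigator.

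**Withdrawal (10.6).** The section goes on to say that "the investigator may discontinue a participant from the trial at any time if the investigator considers it necessary". To such a case it carries over its rule on data, with the words "where the above in relation to data collection will also apply". The data rule just before it is that "any data collected until this point will be retained, analysed and used in the final analysis, but no further data will be collected". The withdrawal is from the trial, not only from the transfusion strategy, and no criteria are given.

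**Analysis sets (16.2).** "The ITT population consists of all patients who underwent randomisation and subsequent cardiac surgery with available outcome data". The per-protocol set separately excludes "patients who were withdrawn from the trial by the treating physician at any time"; the ITT definition does not name such patients.

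Three further points of context. On blinding, section 10.4 states: "The trial allocations cannot feasibly be blinded, and therefore this is designed as an open label trial". The primary test is an unadjusted chi-squared test (16.4). If more than 5% of primary outcomes are missing, "we will develop a missing data model and perform a multiple imputation analysis", together with inverse-probability weighting (16.9).

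**The concern.** The two follow-up rules in 10.6 cannot both be applied to an operated patient whom the investigator withdraws but who has not withdrawn consent. Under one the patient is followed to 6 months; under the other, data collection stops.

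The choice matters because of 16.2. A set conditional on available outcomes is a complete-case set, whatever its label. A patient withdrawn while deteriorating, before a death, infarction, dialysis or stroke is recorded, has no 6-month outcome and can drop out of the primary comparison. The person who may withdraw the patient knows the allocation, so such losses can differ by arm. Blinded adjudication does not help with events that were never collected, and an unadjusted test does nothing to offset selective loss. If the losses are few, 16.9 brings no second analysis into play.

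**Working it through.** **1. Side-by-side reading of the text**

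| Situation of an operated patient | Follow-up rule in 10.6 and 18.1.2 | Investigator sentence in 10.6 | Place in the 16.2 ITT set |
|---|---|---|---|
| Participant withdraws consent for follow-up | Ends | Not relevant | Depends on outcome data held |
| Investigator withdraws the patient after an event is recorded | Continues | Ends | Stays, since earlier data are kept |
| Investigator withdraws the patient before any event is recorded | Continues | Ends | Can leave |

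The last row is the gap.

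**2. The plan's own figure**

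Inputs from 16.1 and 16.6: 14% against 20%, 1,440 patients, 1.5% lost, final critical Z of 1.98. Evaluable per arm: 720 × 0.985 ≈ 709.

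Power = Φ[(d − 1.98 × SE0) / SE1], where d is the risk difference (restrictive minus liberal), SE0 uses the pooled risk and SE1 the separate risks.

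- SE0 = √(0.17 × 0.83 × 2/709) = 0.01995
- SE1 = √(0.20 × 0.80/709 + 0.14 × 0.86/709) = 0.01989
- (0.06 − 1.98 × 0.01995)/0.01989 = 1.03, so power is 84.9%, against the stated 85%. The figure is reproduced.

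**3. Illustration: restrictive-arm losses with the planned effect true**

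The documents give no number of withdrawals and no event risk for withdrawn patients. Both are assumed here: 14 patients (about 2% of 709) with a 50% event risk, hence 7 events lost.

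- Observed restrictive risk = (141.8 − 7)/(709 − 14) = 19.4%
- Risk difference 5.4 points instead of 6.0
- Power **76.8%**
- Range: 7 patients at 40% risk, 82.4%; 21 patients at 60% risk, 66.8%

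Two variants of the central case:

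- Half the events (3.5) already recorded, and those patients kept: (141.8 − 3.5)/(709 − 10.5) = 19.8%, power **82%**
- The same 14 patients and 7 events lost in both arms: 19.4% against (99.26 − 7)/695 = 13.3%, power **87%**, so no loss

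**4. Illustration: liberal-arm losses with no true effect**

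Take 17% in both arms, the midpoint of the planning rates. The liberal risk becomes (120.53 − 7)/695 = 16.3%, a spurious difference of about 0.7 points. The chance of wrongly favouring liberal rises from 2.4% to **5.0%** (range 3.1% to 9.4% over the same assumptions as in step 3).

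**5. Would 16.9 respond?**

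The trigger is 5% of 1,440 = 72 patients. Planned attrition is 1.5%, about 22. Adding 14 gives 36, or 2.5%, so the trigger is not reached. At the 4.5% loss that 18.1.2 reports for the preceding trial, 65 + 14 = 79 would reach it.

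**The case against.** The case on the other side has real weight.

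- **Clinicians have other ways to respond.** Section 11.1 allows a temporarily raised trigger in severe physiologic derangement. Section 11.6 allows suspension for bleeding and keeps those patients in the trial. Section 11.5.2 records off-strategy transfusion as non-adherence without requiring withdrawal. This stands: it reduces the need to withdraw, though it does not remove the power to do so.
- **Events before withdrawal count.** Section 10.6 retains them. Section 10.7 requires deaths to be reported, and ONS linkage (14.12.2, 19.4) adds UK mortality. The first part stands fully. The death provisions are not reconciled with the stop on data collection, and ONS mortality covers neither the non-fatal components nor patients outside the UK, where 320 are planned.
- **ITT was probably meant to keep these patients,** because physician withdrawal is named only for the per-protocol set. That is a fair reading of intent, but the outcome-data condition still removes those without an outcome.
- **The illustration is one-sided.** It puts all losses in one arm and adds them to the planned attrition. It also uses 1,440, while sections 4 and 7.1 give 1,760; at that size, 2% withdrawn at 50% risk leaves about 85% power. This stands, and is why the figures show a possibility and not an expectation.

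A reader might also infer that 16.2 and 16.9 flatly contradict each other, since a set defined by available outcomes has none missing. That goes too far. A complete-case primary analysis with conditional imputation beside it is coherent. The faults are the ITT label and the 5% condition.

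**Conclusion.** The point holds as an internal contradiction with a possible consequence for the primary analysis. Section 10.6 gives two incompatible rules for operated patients whom the investigator withdraws, one of which also conflicts with 18.1.2. Section 16.2 can then exclude those withdrawn before an event is recorded.

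On assumed withdrawals at 1,440 patients, the central illustration is a fall in power from 85% to 77% if only the restrictive arm is affected, or a rise in the false-positive chance from 2.4% to 5.0% if only the liberal arm is. The first effect shrinks to 82% if half the events were already recorded and disappears if both arms lose equally.

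Two stronger conclusions are tempting and unsupported. One is that deteriorating patients will in fact be withdrawn by arm: the documents give no such figure, and the provisions in section 11 work against it. The other is that the bias would hide harm from the restrictive strategy: it could equally create a false benefit for the liberal one. Neither size nor direction can be determined from the protocol.

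**What to change.** **Section 10.6.** Reconcile the sentences so that an investigator's decision to stop the assigned strategy does not end outcome follow-up, and only the participant's withdrawal of consent for follow-up does. This agrees with 18.1.2 and leaves the transfusion rules untouched.

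**Section 16.2.** Define the primary set as all randomised participants who had cardiac surgery, analysed as allocated, and call it modified ITT. Drop outcome availability from the definition and treat unavailable outcomes as missing data.

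**Section 16.9.** Run the imputation and weighting methods as a sensitivity analysis even when 5% or fewer of the outcomes are missing.

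The cost is a wording amendment, a few extra follow-up contacts and a small amount of analysis work. The planned sample size does not change. The amendment should come early, because outcomes that were never collected cannot reliably be recovered by later analysis.

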#### 10.7 Participant death

All participant deaths must be reported in the eCRF, including the cause of the death.

If a participant dies while in hospital prior to postoperative day 28, all data up to the time of death will be collected in the eCRF, and the clinical event will be reported in both the "Clinical Events" form and the 'Hospital Summary' form. In this case, the 6 month follow-up visit forms will not need to be completed.

#### 10.8 Concomitant Treatment

There are no other trial related restrictions on concomitant medications, treatments or procedures.

#### 11. Trial intervention

#### 11.1 Description of the Trial Intervention/Transfusion Strategies

Trial participants will be randomised to one of the following transfusion strategies in a 1:1 manner:

• **Group 1: Restrictive transfusion strategy:** patients will receive a RBC transfusion if their Hb concentration is <75 g/L (<7.5 g/dL; <4.7 mmol/L) intraoperatively and/or postoperatively.

Page **24** of **55** 

IRAS ID: 325425

• **Group 2: Liberal transfusion strategy:** patients will receive a RBC transfusion if their Hb concentration is <95 g/L (<9.5 g/dL; <5.9 mmol/L) intraoperatively, or postoperatively in the ICU; or <85 g/L (<8.5 g/dL; <5.3 mmol/L) on the ward.

The trial period for intervention will commence on induction of anaesthesia for the index cardiac surgery. When the appropriate Hb trigger is reached, patients in each group will have one unit of RBCs administered followed by repeat determination of the Hb concentration. Each group will be transfused only if their Hb concentration falls below the transfusion threshold. The Hb should be checked before each unit of blood.

The RBC transfusion must take place within the following time frame after the time that the trigger Hb was measured: 2 hours (for patients in the operating room (OR)), 18 hours (in the ICU/Cardiac Care Unit (CCU) or other intensive care environment, including step-down units), or 40 hours (on the hospital ward).

If the investigator decides to perform another intervention, for example re-measuring the Hb or haemoconcentration, and a second Hb value is measured above the trigger within the protocol defined time period (2, 18 or 40 hours, as above), then a transfusion is not required and this would still be considered an adherent "trigger event" (see section 11.5).

Although it is desirable to adhere to the standard triggers, the assigned Hb trigger can be increased to 80 g/L (8.0 g/dL; 5.0 mmol/L) in the restrictive transfusion group or 100 g/L [(10.0 g/dL; 6.2 mmol/L) intraoperative/ICU] / 90 g/L [(9.0 g/dL; 5.6 mmol/L) on the ward] in the liberal transfusion group during an episode of any of the following severe physiologic derangements:

- Mixed/central venous or cerebral oxygen saturation <50%
- Lactate > 4 mmol/L in the absence of the use of epinephrine
- Definitive clinical evidence of active myocardial ischemia as defined by the 4th Universal Definition
- Severe organ dysfunction or failure (heart, kidney, or brain) despite use of two or more inotropic agents or a mechanical circulatory assist device (examples include refractory heart failure or cardiogenic shock, anuria or impending dialysis, or severe neurologic dysfunction requiring acute intervention).

The Hb trigger can be increased due to physiologic derangements above for a maximum of 48 hours or until the physiologic derangement improves, whichever occurs first. After 48 hours, the originally assigned trigger will be resumed and all RBC transfusion administered outside of the assigned strategy will be considered non-adherent.

#### 11.2 Protocol deviations

Adherence to the transfusion triggers will be tracked in the eCRF.

Minor protocol deviations (i.e., out-of-window visit for the 6-month follow-up, labs not performed) or major protocol deviations (i.e., improper consent procedure, serious or systematic errors in applying the transfusion triggers) should be documented appropriately on the Protocol Deviation Log and reported to the DCC via [contact] (with [contact] copied in) within 24 hours.

Page **25** of **55** 

IRAS ID: 325425

#### 11.3 Duration of Intervention

The assigned transfusion strategy will be applied starting from the time the patient enters the OR for the index cardiac surgical procedure, and will be continued until hospital discharge (based on the index cardiac surgery).

Patients who return to the ICU or the OR after being transferred to the ward in the liberal strategy group will be transfused according to the transfusion strategy for those settings (i.e.<95 g/L; <9.5 g/dL; <5.9 mmol/L).

#### 11.4 Measurement of Haemoglobin

While central laboratory measurement of Hb is preferred, any validated method for determining Hb (using co-oximetry, spectrophotometry) may be used for the purpose of determining transfusion triggers and measuring post-transfusion Hb values (e.g., central laboratory, blood gas machine, approved point-of-care.) Sites may check with the coordination centre (CC) if there is any uncertainty about approved point-of-care testing.

#### 11.5 Adherence to Transfusion Strategy and "Trigger Events"

A "trigger event" is defined as follows: an occurrence which starts when a Hb value is measured below the assigned trigger for the first time since any previous event, and ending either (1) when a RBC transfusion is administered, or (2) a Hb value is recorded above the assigned threshold, or (3) after the protocol-defined time period of 2 hours (in the OR), 18 hours (in the ICU/CCU), or 40 hours (on the ward), whichever comes first.

All "trigger events" will be recorded in the eCRF.

#### 11.5.1 Adherent events

At the trigger event level, adherence will be considered to have occurred if

- 1) a RBC transfusion is started within the protocol-defined time period, or
- 2) a Hb value above the threshold is measured within the protocol-defined period.

#### 11.5.2 Non-adherent events

Non-adherence will be considered to have occurred if:

- 1) a RBC transfusion is given without a protocol-defined Hb trigger being met, or
- 2) a RBC transfusion is not given subsequent to a "trigger event", and the Hb remains below the threshold at the end of the protocol-defined period (or a repeated Hb value was not performed during the protocol-defined time period).

In the event that two (or more) units of RBCs are administered in parallel or immediately consecutively, without measuring the Hb value between units, and if the first Hb value measured after the RBC transfusion of these multiple units is still lower than the transfusion trigger, then the administration of each unit will be considered adherent. If the first Hb value after the transfusion of these multiple RBC units is above the trigger, then the initial RBC transfusion would be considered adherent, and any additional units given after the initial unit (and before any subsequent Hb measurements) would be considered non-adherent.

Adherence to transfusion strategies will be closely monitored throughout the trial, and it is expected that sites will maintain an acceptable adherence rate.

#### 11.6 Temporary Protocol Suspensions

Patients who have rapid blood loss, or are hemodynamically unstable (e.g., a systolic blood pressure <80 mmHg or the need of two or more inotropes) due to blood loss, can be transfused RBCs at the discretion of the attending physician, and the protocol may be temporarily suspended. These patients will not be withdrawn from the trial. The protocol will be resumed immediately after such an event and RBC transfusions administered during this time will not be considered a breach of protocol or non-adherent (although all transfusions will be recorded in the eCRF). The RBC transfusion protocol can be suspended for acute bleeding for a maximum of 24 hours or until surgical haemostasis, whichever occurs first. After 24 hours, the protocol will be resumed and all RBC transfusion administered outside of the assigned strategy will be considered non-adherent.

#### 11.7 Other (non-red-cell) Transfusions

Other blood products may be administered based on institutional protocols but should require the presence of ongoing bleeding and/or documented measurement of abnormal coagulation. The non-RBC product transfusions should be targeted toward the haemostatic abnormality in accordance with published guidelines and generally accepted practice. Plasma (15 ml/kg) or Prothrombin Complex Concentrate should be considered in the presence of haemorrhage with an international normalized ratio (INR) >1.5 if there is ongoing bleeding. Cryoprecipitate or fibrinogen concentrate is suggested in the presence of bleeding and a fibrinogen concentration <1.5 g/L. Platelet transfusion should be considered when there is bleeding with a platelet count less than 80,000 x 109/L or in the presence of documented abnormalities of platelet function. Information about non red-cell and haemostatic factor concentrate transfusions will be collected in the eCRF (e.g., platelets, rFVIIa, fibrinogen concentrate, prothrombin complex concentrates).

#### 11.8 Patient blood management

Patient blood management (PBM) describes the application of personalised, evidence-based, care bundles of interventions that reduce bleeding and transfusion in people undergoing cardiac surgery, with the intention of improving clinical outcomes. PBM is recommended by current guidelines but implementation is variable. A network meta-analysis of 393 RCTs failed to demonstrate an interaction between transfusion thresholds and 4 other PBM interventions; pre-surgery iron therapy, cell salvage and autotransfusion, tranexamic acid, and point-of-care viscoelastic testing, with respect to transfusion, organ injury or death. A post-hoc analyses of TRICS III data also failed to demonstrate an interaction between countries where PBM is/ is not considered the standard of care on transfusion rates or outcomes. For example, in Germany where PBM is considered the standard of care, transfusion rates and outcomes were similar to the results for the TRICS III trial overall ([name], personal communication). For this reason, and given the wide range of healthcare resources across the countries recruiting to TRICS IV, we have not mandated a PBM protocol beyond best local care, although the nature of these interventions will be recorded. This will provide information on the generalisability of the trial findings in both richer/poorer and PBM intensive/less intensive healthcare settings. The threshold for red cell transfusion is also integral to any PBM care bundle, and the results of TRICS IV will inform evidence based PBM strategies.

# 12. Screening and eligibility

#### 12.1 Screening and eligibility

All local regulations should be followed as they pertain to screening activities. Potential participants will generally be identified from the cardiac surgical schedule, or in the preoperative anaesthesia or cardiac surgery clinics or ward at each hospital where informed consent will be obtained. Initial eligibility may be assessed through a review of the medical chart or discussion with the patient and if

the patient appears to meet the eligibility criteria, the consent process may be initiated. No trial assessments (including a pregnancy test done for trial eligibility purposes only) may be carried out prior to obtaining informed consent.

Co-enrolment into other observational (non-interventional) studies is generally acceptable as long as this is approved by the local ethics committee.

Co-enrolment into other interventional research studies should be discussed in advance with and approved by the DCC/Sponsor.

#### 12.2 Screening log

A screening log template will be provided by the DCC prior to site activation, and this should be maintained at each site. The screening log will capture information about every patient actively screened for the trial and will collect (a) the reason for ineligibility; or (b) if eligible, whether randomised or not (and if not randomised, why not). Sites should also record **the total number of cardiac surgeries done, on bypass, every month.** 

All patients recorded on the screening log will be assigned a screening ID (i.e. S-01, S-02, S-03, etc.), however only patients who are fully eligible, have signed the ICF, and are ready to be randomised should be entered in the eCRF and assigned a participant ID.

Each site is requested to submit the cumulative screening log, along with the data corresponding to the total number of cardiac surgeries performed, on bypass, to the DCC via [contact] (with [contact] copied in) by the first weekday of each month. The DCC may request the screening log more frequently if necessary to review screening activities.

